4.3. Replacement of Subjects

Subjects who withdraw from the study or whose randomization code has been broken will not be replaced.

4.4. Unblinding of Treatment Assignment

The Sponsor and all subjects, monitors, and Study Center personnel will be blinded throughout the study. However, if a subject has suffered a Serious Adverse Event (SAE) (as defined in Section 9.3.3), and/or when knowledge of the treatment assignment will impact the clinical management of the subject, the Investigator will have the ability to unblind the treatment assignment for that subject using the automated IRT system. The Sponsor or designee will be informed of the unblinding of a subject within 24 hours. An unblinded randomization schema will be maintained securely at the Sponsor's designated vendor. In addition, all SUSARs will be unblinded by the Sponsor or designee for the purpose of regulatory reporting (see Section 9.2).

Every reasonable attempt should be made to complete the early termination study procedures and observations (see Appendix A and Appendix B) prior to unblinding, as knowledge of the treatment arm could influence subject assessment.

5. SUBJECT ELIGIBILITY

To be eligible to participate in this study candidates must meet the following eligibility criteria within 28 days of Study Day 1 or at the time point specified in the individual eligibility criterion listed.

5.1. Inclusion Criteria

1. Must have given written informed consent (signed and dated) and any authorizations required by local law and be able to comply with all study requirements
2. Males or females aged 18-72 inclusive and weighing $\geq 50 \text{ kg}$ at the time of informed consent

3. Satisfy the following:
 - a. Females: must be non-pregnant and non-lactating, and either:
 - i. surgically sterile (e.g., tubal occlusion, hysterectomy, bilateral salpingectomy, bilateral oophorectomy) or,
 - ii. post-menopausal (defined as 12 months of spontaneous amenorrhea in females > 55 years of age or, in females ≤ 55 years, 12 months of spontaneous amenorrhea without an alternative medical cause and follicle stimulating hormone (FSH) levels in the postmenopausal range for the laboratory involved)
 - b. Males: Surgically sterile (i.e., bilateral orchidectomy) or abstinent*, if engaged in sexual relations with a woman of child-bearing potential (WOCBP), the subject or subject's non-pregnant female partner must be using a highly effective contraceptive method (refer to Section 6.3.1) from the time of signing the informed consent form until at least 13 weeks after the last dose of Study Drug (ISIS 757456 or placebo)

* True abstinence (i.e., refraining from heterosexual intercourse throughout the duration of study participation) is only acceptable. Periodic abstinence (e.g., calendar, ovulation, symptothermal, post-ovulation methods), declaration of abstinence for the duration of a trial and withdrawal are not acceptable methods of contraception
4. Willing to refrain from strenuous exercise/activity (e.g., heavy lifting, weight training, intense aerobics classes, etc.) for at least 24 hrs prior to study visits
5. BMI ≤ 35.0 kg/m²
6. Brachial circumference is ≥ 22 and ≤ 37 cm (8.7 and 14.6 inches)
7. Subject must have been diagnosed with essential hypertension for a minimum of 3 months prior to screening
8. At Screening, the subject must have a plasma AGT concentration ≥ 20 µg/mL
9. At Screening, the subject must have been on a stable regimen of antihypertensive medications (a total of 2) for at least 1 month prior to screening, using either an angiotensin-converting enzyme inhibitor (ACEi) or an angiotensin II receptor blocker (ARB), as well as a single other antihypertensive medication in the following categories:
 - a. beta blocker
 - i. acebutolol (≤ 400 mg q.d.)
 - ii. atenolol (≤ 50 mg q.d.)
 - iii. betaxolol (≤ 10 mg q.d.)
 - iv. bisoprolol (≤ 5 mg q.d.)
 - v. carvedilol (≤ 25 mg b.i.d.)
 - vi. labetalol (≤ 200 mg b.i.d.)
 - vii. metoprolol (≤ 100 mg q.d.)
 - viii. nadolol (≤ 40 mg q.d.)

- ix. nebivolol (≤ 10 mg q.d.)
 - x. propranolol (≤ 120 mg q.d.)
 - xi. pindolol (≤ 5 mg b.i.d.)
- b. calcium channel blocker or
 - c. diuretic
10. At Screening, the average office seated BP must be within ≤ 140 mmHg systolic and ≤ 90 mmHg diastolic. The average is to be derived from 3 assessments taken within 10 minutes. Up to 2 additional tests allowed in order to qualify
 11. On Study Day -7, the average office seated systolic blood pressure (SBP) must be within the following ranges with $> 140 - \leq 165$ mmHg. The average is to be derived from 3 assessments taken within 10 minutes. Up to 2 additional tests allowed for eligibility purposes
 12. In the opinion of the Investigator, the subject could be safely withdrawn from antihypertensive therapy for at least 12 weeks
 13. Agree to conduct at home BP and HR monitoring (in triplicate using study provided device) thrice weekly and document the average of the triplicate measurements assessed on a day in the patient diary
 14. Agree to abstain from alcoholic beverages for at least 24 hours prior to clinic visits
 15. Agree to maintain adequate hydration and current diet regimen
 16. Agree to abstain from smoking, exercise, and caffeine use 30 minutes prior to blood pressure measurements.

5.2. Exclusion Criteria

1. Clinically-significant abnormalities in medical history (e.g., previous acute coronary syndrome within 6 months of screening, major surgery within 3 months of screening, type I diabetes mellitus) or physical examination
2. Unwilling to discontinue antihypertensive medications during WO and Treatment Period of study
3. Subject has a history of secondary hypertension
4. Subject with borderline orthostatic hypotension (assessed at Screening), when they assume a standing position (within 3 minutes of standing up), defined as:
 - a. A decrease in SBP of ≥ 17 mmHg or
 - b. A decrease in diastolic blood pressure (DBP) of ≥ 7 mmHg
5. The use of the following at time of screening and during the course of the study:
 - a. Other medications for the treatment of hypertension (e.g., clonidine, guanfacine, guanabenz, alpha-methyldopa, hydralazine, minoxidil, diazoxide, renin inhibitors)

- b. Medications that also may cause hyperkalemia (e.g., cyclosporine or tacrolimus, pentamidine, trimethoprim-sulfamethoxazole, all heparins)
 - c. Oral or subcutaneous anticoagulants (e.g., warfarin, rivaroxaban, apixaban, heparin, lovenox)
 - d. Organic nitrate preparations (e.g., nitroglycerin, isosorbide mononitrate, isosorbide dinitrate, or pentaerythritol)
 - e. Sildenafil, tadalafil, vardenafil
6. Treatment with another Study Drug, biological agent, or device within 1 month of screening, or 5 half-lives of study agent, whichever is longer
 7. Previous treatment with an oligonucleotide or other RNA therapeutic (including siRNA) within 4 months of screening if single-dose received, or within 12 months of screening if multiple doses received
 8. Known history of or positive test for human immunodeficiency virus, hepatitis C, or chronic hepatitis B
 9. Malignancy within 5 years, except for basal or squamous cell carcinoma of the skin or carcinoma *in situ* of the cervix that has been successfully treated. Subjects with a history of other malignancies that have been treated with curative intent and which have no recurrence within 5 years may also be eligible if reviewed by the Sponsor Medical Monitor
 10. History of bleeding diathesis, coagulopathy, immune thrombocytopenic purpura (ITP), thrombotic cytopenic purpura (TTP), or any qualitative or quantitative platelet defect
 11. Recent history of or current drug or alcohol abuse that could impact study compliance
 12. Unstable/underlying cardiovascular disease defined as:
 - a. Any history of congestive heart failure (NYHA class II-IV)
 - b. Any history of previous stroke, transient ischemic attack, unstable or stable angina pectoris, or myocardial infarction prior to screening
 - c. 12-lead ECG demonstrating a QT interval (corrected using Fridericia's formula [QTcF]) > 450 msec in males and > 470 msec in females at Screening, or a history or evidence of long QT syndrome
 - d. Any clinically-significant active atrial or ventricular arrhythmias
 - e. Any history of coronary bypass or percutaneous coronary intervention
 13. Active infection requiring systemic antiviral or antimicrobial therapy that will not be completed prior to Study Day 1
 14. Show evidence of uncorrected hypothyroidism or hyperthyroidism hormone results at Screening. Subjects receiving dose-stable thyroid replacement therapy for at least 3 months prior to screening will be allowed to participate as long as thyroid tests (TSH/T3/T4) show that patient is euthyroid

16. Appendices

ISIS 757456-CS2
Protocol

CONFIDENTIAL

Amendment 1
29 March 2019

15. Screening laboratory results as follows, or any other clinically-significant abnormalities in screening laboratory values that would render a subject unsuitable for inclusion
 - a. Urine protein/creatinine (P/C) ratio ≥ 0.3 mg/mg. In the event of P/C ratio above this threshold eligibility may be confirmed by a quantitative total urine protein measurement of < 300 mg/24 hr
 - b. Positive test (including trace) for blood on urinalysis. In the event of a positive test eligibility may be confirmed with urine microscopy showing ≤ 5 red blood cells per high power field
 - c. Alanine aminotransferase (ALT), aspartate aminotransferase, bilirubin, alkaline phosphatase (ALP), serum creatinine, blood urea nitrogen (BUN) > 1.5 x upper limit of normal (ULN)
 - d. Platelet count $<$ Lower Limit of Normal (LLN)
 - e. Serum potassium > 4.85 mmol/L
 - f. Estimated glomerular filtration rate (eGFR) of less than 60 mL/min/ 1.73 m² using the Chronic Kidney Disease Epidemiology Collaboration formula
16. Clinically significant abnormalities upon physical examination which in the Investigator's opinion should exclude the subject from study participation
17. Subject works night time shifts (e.g., 11 PM to 7 AM)
18. Blood donation of 50 to 499 mL within 30 days of screening or of > 499 mL within 60 days of screening
19. Have any other conditions, which, in the opinion of the Investigator or Sponsor would make the subject unsuitable for inclusion, or could interfere with the subject participating in or completing the study
20. Unwilling to comply with study procedures, including follow-up, as specified by this protocol, or unwillingness to cooperate fully with the Investigator

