6.1.1. Screening

Written informed consent for the study will be obtained prior to the performance of any study-related procedures including screening procedures. A 3-week period is provided for completing screening assessments and determining subject eligibility for the study. Safety labs may be re-tested up to 2 additional times for determination of subject eligibility after consultation with the Sponsor Medical Monitor.

During the Screening Period, subjects will undergo a medical history (including cardiovascular disease risk factors) and physical examination including vital signs, orthostatic hypotension assessment, 12-lead ECG, and have blood and urine samples taken for clinical laboratory testing. Subjects will be screened for HIV, HepB, and HCV.

The study site will record basic personal details about the subject, including the subject's name, contact details, gender, height, weight, date of birth, age, ethnicity, and racial origin (to be used only for clinical purposes), as well as information on the subject's medical history, and clinical data collected about the subject's participation in the study.

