8.5. Safety Monitoring Rules

Please refer also to the 'Guidance for Investigator' section of the ISIS 757456 Investigator's Brochure.

In addition to the standard monitoring of clinical safety parameters, the following guidelines are provided for the monitoring of selected parameters chosen based on preclinical and clinical observations.

Confirmation Guidance: At any time during the Study (Treatment or Post-Treatment Periods), the initial clinical laboratory results meeting the safety monitoring criteria presented below must be confirmed by performing measurements (ideally in the same laboratory that performed the initial measurement) on new specimens. All new specimen collections should take place as soon as possible (ideally within 3 days of the initial collection). For stopping rules, if the initial laboratory result is observed during the Treatment Period, the results from the retest must be available prior to administering the next dose of Study Drug (ISIS 757456 or placebo).

Re-dosing Guidance: Subjects with initial laboratory test values that reach a stopping rule must not be re-dosed until the re-test results are available. In general, subjects who do not meet the stopping rules based upon retest may continue dosing. However, the Investigator and the Sponsor Medical Monitor (or appropriately qualified designee) should confer as to whether additional close monitoring of the subject is appropriate. If any of the stopping criteria described below (refer to Section 8.6.1 to Section 8.6.5) are met, the subject will be permanently discontinued from further treatment with Study Drug (ISIS 757456 or placebo), evaluated fully as outlined below and in consultation with the Sponsor Medical Monitor or appropriately qualified designee, and will be followed-up in accordance with Section 8.8.

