8.6.2. Stopping Rules for Renal Function Test Results

In the event of laboratory results for either of the following criteria, dosing of a subject with Study Drug (ISIS 757456 or placebo) will be stopped permanently:

1. Confirmed serum creatinine increase that is both ≥ 0.3 mg/dL (26.5 μ mol/L) and $\geq 40\%$ above Baseline creatinine values (refer to Definition of Baseline in Section 8.6)
2. Confirmed 30% decline in eGFR from Baseline eGFR values
3. Confirmed proteinuria (UPCR ≥ 500 mg/g)

The follow-up schedule for any events meeting either of these stopping criteria will be determined by the Investigator **in consultation with** the Sponsor Medical Monitor or designee. At the discretion of the Investigator, a decision to hold or permanently stop study drug may be made based on lesser changes in these parameters observed in isolation or in association with other renal-related abnormalities.

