10.3. Populations

Full Analysis Set (FAS): All randomized subjects who have received at least 1 injection of Study Drug (ISIS 757456 or Placebo) and who have at least 1 post-Baseline efficacy or exploratory measurements.

Per Protocol Set (PPS): All FAS subjects who received at least 5 of the 7 doses of Study Drug, did not receive antihypertensive medications during the Treatment Period and prior to Study Day 43, and have no significant protocol deviations that would be expected to affect efficacy or exploratory assessments.

Safety Set: All subjects who are randomized and receive at least 1 dose of Study Drug.

PK Set: All subjects who are randomized and receive at least 1 dose of Study Drug and have at least 1 evaluable PK sample.

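### The 24-hour urine override in exclusion 15a has no ceiling on spot UPCR, so a subject can enter at or above the level that permanently stops dosing

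*Combined protocol and SAP*

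**What the plan says.** **Entry.** Criterion 15a, in the protocol synopsis and in Section 5.2, excludes "Urine protein/creatinine (P/C) ratio ≥ 0.3 mg/mg". It continues: "In the event of P/C ratio above this threshold eligibility may be confirmed by a quantitative total urine protein measurement of" less than 300 mg/24 hr. No maximum is given for the spot ratio when this route is used. Section 6.1.1 adds that "Safety labs may be re-tested up to 2 additional times for determination of subject eligibility", after consultation with the Medical Monitor.

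**On study.** Section 8.6.2 lists three renal criteria under which "dosing of a subject with Study Drug (ISIS 757456 or placebo) will be stopped permanently". The creatinine and eGFR criteria are changes from Baseline. The third is an absolute level: "Confirmed proteinuria (UPCR ≥ 500 mg/g").

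**Confirmation and holds.** Section 8.5 confirms a result by repeating the measurement on a new specimen and does not ask for a 24-hour collection. It also says: "Subjects with initial laboratory test values that reach a stopping rule must not be re-dosed until the re-test results are available".

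**Schedule.** Appendix A has urinalysis, which includes UPCR (Appendix B), at Screening and then not until Day 1 pre-dose. Day -7, when eligibility is rechecked (Section 6.1.3), has none.

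**Analysis set.** The primary analysis uses the Per Protocol Set (protocol 10.6.3, SAP 3.5.1). Section 10.3 restricts that set to "All FAS subjects who received at least 5 of the 7 doses of Study Drug", with further conditions. Section 4.3 rules out replacing subjects who withdraw.

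**The concern.** The entry rule accepts a high spot ratio that a 24-hour collection contradicts. The stopping rule acts on the spot ratio alone. The two rules are not reconciled in the protocol or the SAP, so the discordance forgiven at entry is not forgiven during treatment.

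Elsewhere the protocol keeps the entry limit inside the absolute action level. Potassium must be at most 4.85 mmol/L to enter, with a hold at 5.5 and a stop at 6.0. ALT and AST must be at most 1.5 x ULN, with monitoring above 3 x ULN. Systolic pressure on Day -7 must be at most 165 mmHg, with withdrawal from treatment above 170. UPCR is the exception.

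A subject admitted this way would be washed out of two antihypertensives and dosed at least once. If the ratio persisted, dosing would be held and, on confirmation, stopped for good. That stop could be read as a renal finding on treatment when it only repeats the entry value. It could also cost a subject in the primary analysis of a small trial.

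**Working it through.** The plan gives no figure to reproduce. The check is a unit conversion, a bound on who can meet both conditions, and a dose count.

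**1. Common units.**
- Entry threshold (5.2, 15a): 0.3 mg/mg x 1000 = 300 mg/g.
- Stopping level (8.6.2): 500 mg/g = 0.5 mg/mg.
- Ratio: 500/300 = 1.67.

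The override applies to any spot value above 300 mg/g, so it includes values of 500 mg/g and more.

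**2. Who can have UPCR of at least 0.5 mg/mg and 24-hour protein below 300 mg.** The 24-hour average ratio is 24-hour protein divided by 24-hour creatinine excretion. If the spot ratio equals that average, both conditions hold only when creatinine excretion is below 300/0.5 = 600 mg/day.
- At the 50 kg entry minimum: 600/50 = 12.0 mg/kg/day.
- At an assumed 80 kg: 600/80 = 7.5 mg/kg/day.

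The documents do not give creatinine excretion, so the table covers an assumed range. The ceiling on the average ratio is 300 mg divided by excretion in g. The factor is 500 divided by that ceiling, and the spot ratio must exceed its 24-hour average by more than this factor.

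| Creatinine excretion (g/day, assumed) | 24-hour average UPCR is below (mg/g) | Factor |
|---|---|---|
| 0.5 | 600 | 0.83 (no discordance needed) |
| 0.6 | 500 | 1.00 |
| 0.8 | 375 | 1.33 |
| 1.0 | 300 | 1.67 |
| 1.2 | 250 | 2.0 |
| 1.5 | 200 | 2.5 |
| 1.8 | 167 | 3.0 |

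Entry at the stopping level is therefore possible in two ways: low creatinine excretion, or a discordant spot sample. In the first the ratio would be expected to recur. In the second it may fall on retest.

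**3. From entry value to stop.** The screening value cannot itself trigger 8.6.2, because confirmation needs a new on-study specimen. The first such specimen is Day 1 pre-dose, after antihypertensive withdrawal. A value of at least 500 mg/g there, or later, blocks the next dose until the retest. A second such value ends dosing.

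**4. Dose count.** Doses fall on Days 1, 3, 8, 15, 22, 29 and 36, so Day 22 is the fifth. The table takes each dose as given on the day its pre-dose sample is drawn.

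| Sample leading to a confirmed stop | Most doses received | At least 5 of 7? |
|---|---|---|
| Day 1 | 1 | No |
| Day 3 | 2 | No |
| Day 8 | 3 | No |
| Day 15 | 4 | No |
| Day 22 | 5 | Yes |

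If the retest clears the subject and only the Day 3 dose is missed, 6 of 7 doses remain and the Per Protocol dose requirement is met.

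**5. Size of one loss.** About 30 subjects at 2:1 gives 20 active and 10 placebo. One subject is 1/20 = 5% of active or 1/10 = 10% of placebo.

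**The case against.** The strongest reply is that a single spot ratio and a confirmed on-study ratio are different things. Criterion 15a does cap protein, at 300 mg/24 h. With creatinine excretion of 1.0 to 1.5 g/day, the subject's true average ratio is below 0.30 to 0.20 mg/mg, well under the stopping level. On this view the override is doing its job, much as microscopy resolves a positive blood test in 15b.

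Harm also needs a chain of events: a high spot at screening, low 24-hour protein, acceptance by the investigator and Medical Monitor, a high ratio again on study, confirmation, and all of it before the fifth dose. The override is permissive. Criterion 19 can exclude anyone with a condition that "could interfere with the subject participating in or completing the study", and Section 4.2 requires Medical Monitor review before randomization. The absolute stop was added on FDA suggestion and is conservative. A stopped subject may stay on study and attend Day 43. That subject remains in the Safety Set and usually in the Full Analysis Set, where AGT change is also compared. Assignment is randomized and blinded, so no bias between arms is claimed.

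Most of this stands, and it limits the size of the problem. It does not remove the gap. None of the discretionary controls states a UPCR limit, so sites may decide differently. The 24-hour result that admits a subject has no standing under 8.6.2. A subject with low creatinine excretion, or with persistent discordance, can be stopped with no change from entry.

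**Conclusion.** The concern holds as a low-magnitude design gap. Read together, 15a and 8.6.2 allow a subject to be randomized and dosed with a spot UPCR already at the level that permanently ends dosing.

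The documents give no frequency, and the expected number may be zero. The bounds rest on assumed creatinine excretion and, for the 7.5 mg/kg/day figure, an assumed weight of 80 kg. The 5% and 10% figures are conditional: they describe the loss if one subject is stopped before Day 22, not a forecast. The cost would be one fewer subject in the primary analysis and a renal stop that is hard to interpret. The correction is cheap enough to be worth making.

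**What to change.** In criterion 15a, in both the synopsis and Section 5.2, allow the 24-hour override only when the screening UPCR, after any retest permitted by Section 6.1.1, is at least 0.3 and below 0.5 mg/mg. A ratio of 0.5 mg/mg or more would exclude the subject whatever the 24-hour result. Leave 8.6.2 unchanged.

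The cost is one clause in two places and, rarely, an extra screen failure in someone whose 24-hour protein is within the limit. The two permitted retests reduce that. The change does not stop a subject just under 0.5 mg/mg from crossing the threshold later through ordinary variation.

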6. STUDY PROCEDURES

6.1. Study Schedule

All required study procedures are outlined in [Appendix A](#), [Appendix B](#) and [Appendix C](#).

The length of each subject's participation in this portion of the study is approximately 5 months that includes a 3-week Screening Period, a 1-week Run-In Period, a 2-week WO Period, a 6-week Treatment Period, and a 13-week Post-Treatment Evaluation Period.

All BP assessments will be conducted according to Section 6.1.1.1 (Seated Blood Pressure Measuring Instructions at Each Visit), Section 6.1.1.2 (Orthostatic Blood Pressure Assessment) and Section 6.1.1.3 (At Home Blood Pressure and Heart Rate Monitoring).

The safety of ISIS 757456 will be continually monitored throughout the trial by the Investigator and the Sponsor Medical Monitor.

